1.1. Study summary

Design

Patients will be randomized to receive either 30mg of atorvastatin or be presented with a choice of receiving either a “natural” statin (red yeast rice extract) or 30mg of atorvastatin.

In the intervention arm, a goal of either LDL-C reduction of at least 50% or an LDL-C < 100 mg/dl will be discussed on the initial visit. Goals will be re-assessed at 2 months, if goals are not met, patients will be given 30mg of atorvastatin.

Aims

To assess if introducing greater patient autonomy increases patient compliance with statin therapy.

Outcome measures

The primary endpoint will be 6-month compliance of statin therapy, after the initiation of atorvastatin.

Secondary endpoints will be rates of perceived side effects from statin use, including myalgias, fatigue, mental fog and GI upset.

Population

This will be a multi-center study of 300 pts, 150 in each arm.

Eligibility

Primary prevention (no history of CAD, MI, or stroke) patients with a moderate 10-year ASCVD risk who decline statin therapy.

Duration

Anticipated recruitment is 6 months. Follow-up will be performed at 6 months in the control arm and 2 and 8 months in the intervention arm, for a total study duration of 14 months.

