1.1. Study overview diagram

4.2 Study protocol:

Patients meeting the study criteria will be enrolled at outpatient cardiology clinics at four centers: Lithuanian University of Health Sciences, Northway Medical Centre, Prienu Hospital, and Unomeda Medical Centre. The enrolment period will last six months, with an estimated 50 patients per month enrolled into the study, for a total of 300 patients.

Patients will be randomized to either the control group or the intervention group. Baseline variables will include demographic variables (age, gender, BMI, blood pressure, heart rate), medical history (hypertension, hyperlipidaemia, type 2 diabetes mellitus, tobacco use), laboratory variables (total cholesterol, HDL, LDL, triglycerides, AST, ALT, creatine kinase, and, vitamin D levels) and socioeconomic variables (education level, income level, rural or urban, and marriage status).

The control group will be provided reassurance through a short, semi-structured discussion on the excellent safety profile of statins, similar to a typical interaction between a clinician and patient. They will then be prescribed 30mg atorvastatin daily as a 30 tablets supply with five patient-initiated re-fills for 30 tablets each. Final follow-up in this group will occur at 6 months.

The intervention group will be offered a red yeast rice extract 20mg nightly to achieve a goal LDL-cholesterol of <2.6 mmol/L (100 mg/dL) in accordance with the 2019 ESC/EAS guidelines (9). Initial follow-up will take place in 2 months to assess the efficacy of their treatment. Patients who are not at the goal LDL-cholesterol will be prescribed 30mg atorvastatin nightly as a 30 tablets supply with five patient-initiated re-fills for 30 tablets each, with final follow-up after 6 additional months. Patients who are at goal on the red yeast rice extract will be recommended to switch to lovastatin 20mg nightly as a bio-identical substitute, but they will be excluded from further analysis.

In both groups, statin adherence will be assessed by pharmacy refill records at the final follow-up. A short, four question questionnaire (Appendix A) will be administered at this point as well. Final follow-up laboratory variables collected will include total cholesterol, HDL, LDL, triglycerides, AST, ALT, creatine kinase, and vitamin D levels.

Conversation guidelines for each clinical encounter in the intervention group are included in Appendix B.

Randomisation

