Appendix B

Clinical Encounter Conversation Guidelines

Control Group Initial Encounter

Point(s) to discuss

1. Acknowledge the patient's reluctance to start statin therapy
2. Reassure the patient that long term data supports the safety of statins
3. Reassure the patient that long term data supports the efficacy of statins

Sample Conversation(s):

"I understand that you are hesitant to start statin therapy. We over two decades of long-term follow-up data regarding statin use. The data clearly shows that statins are extremely safe and patients who stay on statins live longer and healthier lives."

Intervention Group Initial Encounter

Point(s) to discuss

1. Acknowledge the patient's reluctance to start statin therapy

2. ESC/EAS 2019 guidelines recommend an LDL-cholesterol < 2.6 mmol/L (100 mg/dL)
3. Present the option of a natural supplement as an open-ended question
4. The impact of the therapy will be assessed in two months

Sample Conversation(s):

“I understand that you are hesitant to start statin therapy. According to European guidelines, your LDL-cholesterol should be less than 2.6 mmol/L (100 mg/dL) to reduce your risk of a cardiovascular event. What is your opinion on trying a natural supplement to reduce your cholesterol?”

If the patient agrees to red yeast rice extract

“Let's follow up in two months to see if our LDL-cholesterol goals have been met”

Intervention Group Initial Follow-up

If LDL-cholesterol > 2.6 mmol/L (100 mg/dL)

Point(s) to discuss

1. Since the natural remedy did not work, we should switch to the statin to reduce cardiovascular events

Sample Conversation(s):

“Unfortunately, we were not able to meet our goals with the natural supplement. Because of this, let's try the prescription medicine instead (atorvastatin 30mg nightly)”

If LDL-cholesterol < 2.6 mmol/L (100 mg/dL)

Point(s) to discuss

1. The natural remedy did reduce your LDL-cholesterol to our original goal
2. However, the effect of the natural remedy is unreliable over time due to lack of regulation

3. Let's switch to a bio-identical prescription medicine for reliability

“Congratulations, we were able to meet our goal using a natural supplement. This supplement contains naturally occurring lovastatin; however it is difficult to predict the dose that you are receiving since supplements are not regulated. Let's try a medium dose of lovastatin instead (20mg lovastatin nightly)”

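### Section 1.1 makes the intervention a choice between red yeast rice and atorvastatin; 4.2 and Appendix B offer only red yeast rice and leave other responses without a clear route into the refill count

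*Protocol*

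**What the plan says.** Section 1.1 (Study summary), under Design: "Patients will be randomized to receive either 30mg of atorvastatin or be presented with a choice of receiving either a". The sentence ends by naming two options, red yeast rice extract and the control arm's atorvastatin 30 mg.

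Section 4.2 (Study protocol): "The intervention group will be offered a red yeast rice extract 20mg nightly". In that section the intervention arm reaches atorvastatin only at the 2-month visit: "Patients who are not at the goal LDL-cholesterol will be prescribed 30mg atorvastatin nightly as a 30 tablets supply".

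Appendix B, for the first intervention visit, tells the clinician: "Present the option of a natural supplement as an open-ended question". The sample question is "What is your opinion on trying a natural supplement to reduce your cholesterol". The only continuation is headed "If the patient agrees to red yeast rice extract".

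On the endpoint, section 1.1 states: "The primary endpoint will be 6-month compliance of statin therapy, after the initiation of atorvastatin". Section 4.2 has adherence taken from pharmacy records at the final follow-up. Section 4.3 scores each patient 0 to 6 and gives no start or end date. Sections 1.1 (Duration) and 7 place the final visit at month 6 in control and month 8 in the intervention arm, with no exception by what the patient takes.

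**The concern.** The aim is to learn whether more autonomy raises statin compliance, so what the patient is allowed to choose is the intervention itself. A centre working from section 1.1 would put two therapies to the patient. A centre working from Appendix B would put one. With four centres, both could be delivered under one label, and the result could not be attributed to either.

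The second issue follows from the first. Everyone enrolled has already declined a statin, and the appendix asks an open question, so some patients will not simply agree to the supplement. The text does not say what happens to them or how they enter the primary endpoint. If some start atorvastatin on the first day and their refills are counted up to the month-8 visit, they have two months more than control patients in which to collect the same six supplies. That error would favour the intervention.

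**Working it through.** **1. The three passages side by side**

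| Question | 1.1 | 4.2 | Appendix B |
|---|---|---|---|
| Offered at first visit | supplement or atorvastatin | supplement | supplement |
| Atorvastatin can begin | at once by choice, or after the 2-month reassessment | after the 2-month visit, if not at goal | after the 2-month visit, if not at goal |
| Patient who declines the supplement | may choose atorvastatin; nothing on declining both | not stated | not stated |

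The first two rows cannot all be true of one intervention.

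**2. Counting window by type of patient**

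- Accepts the supplement, not at goal at month 2: 8 − 2 = 6 months of atorvastatin by the final visit, the same as control.
- Starts atorvastatin at once (possible only under 1.1): 8 − 0 = 8 months by the visit schedule, but 6 months by the 1.1 endpoint sentence. The two disagree.
- Never starts atorvastatin: no initiation date. The 0–6 scale could give this patient 0, but an endpoint defined after initiation could equally be read as leaving the patient out. The text does not settle it.

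**3. The plan's own figure**

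Inputs from section 4.5: difference 5 points, SD 10, power 0.9, 1:1, total 138.

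n per arm = 2 × (1.645 + 1.282)² × (10/5)² = 68.5, rounded up to 69; 2 × 69 = 138. This reproduces the figure, but only as a one-sided comparison of two means; two-sided gives 85 per arm, 170 in total. Sidedness is a separate matter. What counts here is that the 5 points is a difference in arm means, so any artefact must be put on that scale.

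**4. Illustrative artefact if immediate starters are read at month 8**

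Assumptions not in the protocol: steady use at rate r, months of 30 days, and a share f of the arm starting at once.

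Supplies = min(6, r × days / 30).

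- r = 0.50: 3.0 by day 180 and 4.0 by day 240. As a share of six supplies, 50% and 66.7%, a gain of 16.7 points for that patient.
- r = 0.75: 4.5 and 6.0.
- r = 0.90: 5.4 and 6.0, limited by the cap.

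Shift in arm mean = f × 16.7 at r = 0.50:

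- f = 10%: 1.7 points
- f = 20%: 3.3 points
- f = 30%: 5.0 points

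With whole fills at a fixed gap g, the count by day t is min(6, 1 + floor(t/g)). Between day 180 and day 240 the gain is 0 fills for gaps of 30–36 days, 1 for 37–45, 2 for 46–48, 1 at 60 (4 then 5) and 0 for 81–90. Anyone who stops before day 180 gains none.

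**5. When the artefact vanishes**

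If the 1.1 window is applied, both arms are read over 180 days and the shift is 0. If only red yeast rice is offered, f = 0 and the shift is again 0.

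**6. What keeping everyone in the arm costs**

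Suppose a share f of the intervention arm shows no effect, so that the mean difference is 5 × (1 − f). With 150 per arm, SD 10 and an assumed two-sided 5% level, power is 97%, 93%, 86%, 74% and 58% for f = 10%, 20%, 30%, 40% and 50%. Leaving these patients out keeps power at 94% or more up to f = 50%, so lost numbers are not the problem. The problem is comparing a self-selected part of one arm with all of the other.

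**The case against.** A reader might infer that the protocol has no counting window at all. The text does not support that. Section 1.1 sets six months from atorvastatin initiation, section 4.2 puts the final visit six months after the month-2 prescription, and Appendix A looks back six months. Reading records at the final visit says when they are consulted, not that every fill up to that date counts. This stands. What is left is that the month-8 visit invites the longer count, 4.3 does not repeat the window, and a never-starter has no anchor.

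A reader might also infer that each immediate starter gains one fill, about 17 points, and set that against the 5-point target. That fails too. The gain ranges from 0 to 2 fills with the refill gap, and a change in one patient is not comparable with a difference in arm means unless the share of such patients is known. The protocol gives no share, and because entrants have declined a statin it may be small.

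The artefact also needs both versions at once: the choice from 1.1 together with neglect of the endpoint sentence in 1.1. That is fair, and it is why the figures are only illustrative.

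On the missing branches, it can be said that Appendix B holds guidelines with sample wording and need not be exhaustive; that section 9.2 keeps patients in follow-up and analysis when the clinician gives another treatment; and that analysis sets usually belong in an SAP. But section 4.2 presents the appendix as covering each intervention encounter. Section 9.2 concerns the clinician's departure from protocol, not the patient's answer to the offer, and sets no window. The month-2 rule for patients not at goal could literally reach someone who refused, but that visit exists to judge a treatment presumed taken. What is offered, and what follows a refusal, is protocol content.

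**Conclusion.** The point holds in a limited form. The intervention is defined in two incompatible ways in one document, and for a trial of autonomy that concerns the experimental variable itself. This needs no assumption; it is in the text.

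The endpoint part is narrower. A six-month window is stated in 1.1 but sits uneasily with a final reading fixed at month 8 for the whole intervention arm, and patients who decline the supplement or never start atorvastatin have no start date. The possible bias is about 1.7 to 5.0 points in the arm mean for shares of 10% to 30%, at an assumed 50% use and with the 1.1 window ignored. It is zero if that window is applied. The documents do not show that the bias will occur, only that the wording permits it. The point should be dealt with before enrolment.

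**What to change.** 1. Reconcile section 1.1, section 4.2 and Appendix B on what the intervention arm is offered, and cover in the appendix each answer a patient can give. Which version to keep is for the investigators.
2. State that intervention patients stay in their assigned arm for analysis whatever they accept or decline at the first visit. The separate exclusion in 4.2 of patients at goal on the supplement is not settled by this sentence.
3. State in 4.2 and 4.3 that fills are counted over the same 180 days in both arms, from the atorvastatin prescription or, if it is never started, from its scheduled date, and not up to the month-8 visit. Name that scheduled date once item 1 is decided.

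The cost is wording in the protocol and script. Pharmacy refill records are already the data source; the rule needs dated fills from them. Item 2 may dilute the effect if many patients do not take the supplement, by the amounts in step 6 of the working.

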4.3. Study outcome measures

Primary Endpoint

Rate of statin compliance, based on pharmacy refill records. Values per patient can range from 0-6 according to the number of refills.

Secondary Endpoints:

Rate of perceived side-effects from statin use, including muscle aches, fatigue, mental fog, and gastrointestinal upset.

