4.5. Sample size/Power calculation

This study is designed as a superiority trial. Based on prior literature, we estimate a 50% statin compliance rate with a standard deviation of 10% (2). We will set the minimal detectable effect at a 5% increase in statin compliance, with an $\alpha < 0.05$ and power of 0.9. Based on case-to-control ratio of 1:1, our total minimum sample size for the primary endpoint is 138. However, we will plan on a total sample size of 300 patients, to account for patients who drop out of the study as well as patients who will be excluded due to attaining an LDL-cholesterol of <2.6 mmol/L (100 mg/dL) on red yeast rice extract.

5. Participant entry

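### The primary endpoint starts at atorvastatin initiation, which the two arms reach by different routes after randomisation, and the protocol does not settle how a patient who never starts is scored.

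*Protocol*

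**What the plan says.** - **Endpoint.** Protocol section 1.1: "The primary endpoint will be 6-month compliance of statin therapy, after the initiation of atorvastatin".
- **Route to atorvastatin.** In section 4.2 controls are prescribed it at the initial encounter. For those on red yeast rice, the step follows the 2-month LDL check: "Patients who are not at the goal LDL-cholesterol will be prescribed 30mg atorvastatin nightly". Both arms then have a "30 tablets supply with five patient-initiated re-fills for 30 tablets each", that is, six possible dispensings.
- **Patients at goal at month 2.** They are advised to move to another prescribed statin, "but they will be excluded from further analysis" (4.2).
- **Measurement.** "statin adherence will be assessed by pharmacy refill records at the final follow-up" (4.2). Section 4.3 adds: "Values per patient can range from 0-6 according to the number of refills".
- **Sample size.** Section 4.5 plans on these figures: "we estimate a 50% statin compliance rate with a standard deviation of 10" per cent, a 5-point increase and a minimum of 138. It raises the total to 300, partly "to account for patients who drop out of the study".
- **Population.** Section 5.2 enrols people who decline statins.
- **Departures.** Section 9.2 lets the clinician give other treatment at any stage and keeps such patients in the analysis.

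**The concern.** Starting atorvastatin happens after randomisation, and the arms reach it differently. A control reaches the prescription on day 0. A red yeast rice patient must, on the protocol pathway, stay engaged for two months and then be above goal. If the endpoint exists only for patients who start, early disengagement removes patients from the intervention arm, while the same behaviour in a control produces a low score that stays in. If the patients lost this way are the less adherent ones, the remaining intervention patients look better for reasons unrelated to autonomy.

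The opposite rule, scoring every never-starter 0, charges the same missed visits to the intervention. The sign of the primary result could therefore depend on which rule is used, and the protocol's sections point in different directions.

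**Working it through.** **1. What the sections imply for each type of patient**

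| Patient | 1.1 read literally | 4.3 scale | 4.5 |
|---|---|---|---|
| Control, fills once, stops | low score | low score | – |
| Control, prescribed, never fills | no initiation, so no value | 0, if all dispensings count | lost, if regarded as a dropout |
| Red yeast rice, misses month 2, never prescribed | no value | not addressed | lost, if regarded as a dropout |

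One supply plus five refills makes six. A score of 6 is reachable only if every dispensing counts, so 0 would mean that nothing was dispensed. This supports 0 for a prescribed never-filler but does not reach a patient who was never prescribed.

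**2. The plan's own sample size**

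n per arm = 2(z_α + z_β)²·SD²/δ², with SD 10, δ 5 and power 0.90.
- One-sided 5%: 2 × (1.645 + 1.282)² × 100/25 = 68.5, so 69 per arm and 138 in total. This is the plan's figure.
- Two-sided 5%: 84.1, so 85 per arm and 170 in total.

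The 138 does not depend on this point. It confirms that 50%, 55% and SD 10% are the planning values.

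**3. Effect of the rule at the planning values**

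Assume that intervention starters average 55, that the control arm is fixed at 50, and that a share f of the intervention arm never starts.
- Left out: the difference stays 5.
- Scored 0: the difference is 55(1 - f) - 50. At f = 5% it is 2.25. It reaches 0 at f = 1 - 50/55 = 9.1%.

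**4. Effect of the rule when there is no true difference**

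All rates here are assumed. Underlying adherence p has mean 0.5 and variance V in both arms. Month-2 non-return has probability 2r(1 - p), and control never-filling has probability 2f(1 - p), with averages r and f. Every intervention patient takes red yeast rice, every returner fills, and the at-goal exclusion is ignored.
- Left out: shift = 2V[r/(1 - r) - f/(1 - f)].
- Scored 0: shift = -2(r - f)(0.25 - V).

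V = 0.01 takes the plan's SD of 10% as the SD of underlying adherence. V = 1/12 is uniform adherence.

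Worked at r = 15%, f = 0:
- Left out: 2 × 0.01 × 0.15/0.85 = +0.35 points; 2 × (1/12) × 0.15/0.85 = +2.94 points.
- Scored 0: -0.30 × 0.24 = -7.2 points; -0.30 × 0.1667 = -5.0 points.

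Shifts in percentage points:

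| r | f | Left out, SD 10% | Left out, uniform | Scored 0, SD 10% | Scored 0, uniform |
|---|---|---|---|---|---|
| 5% | 0 | +0.11 | +0.88 | -2.4 | -1.7 |
| 15% | 0 | +0.35 | +2.94 | -7.2 | -5.0 |
| 30% | 0 | +0.86 | +7.14 | -14.4 | -10.0 |
| 5% | 10% | -0.12 | -0.97 | +2.4 | +1.7 |
| 15% | 10% | +0.13 | +1.09 | -2.4 | -1.7 |
| 30% | 10% | +0.63 | +5.29 | -9.6 | -6.7 |

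At r = 15%, f = 0, the two rules differ by 0.35 + 7.2 = 7.55 points or 2.94 + 5.0 = 7.94 points. The planned effect is 5.

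**The case against.** **Handling of dropouts belongs in an analysis plan.** This is often true, and that plan is not shown. Here, however, the protocol itself fixes the endpoint's starting point, at a post-randomisation event that differs by arm. An analysis plan could set one rule for everyone only by overriding 1.1 or extending 4.3.

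**Controls are less ambiguous than they look.** This largely stands. The 0-6 scale gives a prescribed never-filler a natural 0, and the dropouts in 4.5 need not be never-fillers. The unscored group is mainly red yeast rice patients who miss month 2.

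**The numbers are assumed.** This stands. If the SD of adherence is 10%, the shift from leaving never-starters out is below 1 point even at 30% non-return. A reader might infer a badly inflated false-positive rate. With 150 per arm and 15% non-return, simulation does give false significance for the intervention of 3.5% (SD 10%) or 11.1% (uniform), against a nominal 2.5%. That assumes no control never-filling. With 10% of controls never filling and left out, the rates are about 2.8% and 4.4%. The documents support no particular rate.

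**Scoring 0 is contestable.** This also stands as a cost. A non-returner's LDL is unknown, and some might have been at goal.

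Three stronger readings are tempting, but the documents do not support them:
- *Red yeast rice patients can start only by returning at month 2.* Section 9.2 allows clinician departures at any time.
- *Intervention patients who choose atorvastatin at baseline have refills counted over 8 months.* Section 4.2 says when records are read, not how many months count, and 1.1 fixes 6 months.
- *The side-effect comparison is flawed because nothing is asked about months 0-2.* Appendix A puts the same 6-month atorvastatin question to both arms, so that comparison is like for like.

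**Conclusion.** The concern holds for the primary endpoint. Following 1.1 literally restricts the comparison to patients who start atorvastatin, and starting is reached differently by arm. Section 4.3 leans towards scoring a prescribed never-filler 0, 4.5 leans towards losing dropouts, and nothing covers a patient who was never prescribed.

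Neither the direction nor the size of any bias can be derived from the documents, because they give no non-return, never-fill or choice rates. The working shows only that the choice of rule can matter as much as the planned effect. The shifts shrink roughly in proportion to the share of the intervention arm that takes red yeast rice, and control never-filling can offset or reverse them. It would be wrong to conclude that the design is shown to favour the intervention. The point should be corrected before analysis; confidence is medium.

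**What to change.** 1. In 1.1 and 4.3, make the primary analysis as randomised, with one rule for both arms. Count dispensings over 6 months from the actual atorvastatin prescription date. A patient with no dispensing scores 0. This includes a red yeast rice patient never prescribed because month 2 was missed, whose window runs from the scheduled month 2. Using the actual date elsewhere avoids shortening the window for late returners.
2. State that this compares the strategies as offered and is not a bias correction. Report the initiators-only comparison as a sensitivity analysis, with the number of never-starters per arm.
3. State in the same definition how at-goal patients enter, because their exclusion in 4.2 is incompatible with an as-randomised analysis. One option is to count their prescribed-statin dispensings over the same 6 months and show the result without them as a sensitivity analysis.
4. Separately, reconcile 1.1, which offers atorvastatin as a baseline choice, with 4.2, section 7 and Appendix B, which set out no path for those who take it. State that the 6-month window of 1.1 applies to any such patients.

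**Cost.** Protocol wording and one or two sensitivity analyses. Section 4.2 already calls for pharmacy records, and reading them needs no extra visit. The downside to name is that missed month-2 visits count against the intervention, including patients whose LDL status is unknown. In the null model at 15% non-return this is -7.2 to -5.0 points with no control never-filling, and -2.4 to -1.7 if 10% of controls never fill.
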